3.2 Final statistical analysis plan

The primary outcome for efficacy is the rate of symptomatic CSDH ipsilateral recurrences requiring reoperation within 6 months. The statistical analysis for efficacy will be performed according to both the ITT and PP principles. The ITT analysis will be performed using the full analysis set, defined as all randomized patients in the groups allocated by randomization. No exclusions other than those caused by missing information will be made. No imputation will take place. The PP analysis will be performed on the subset of the full analysis set that is compliant with the protocol, has completed treatment, has available measurements, and has no major protocol violations or entry criteria violations.

As the goal of CSDH surgery is not only to prevent reoperations but also to improve neurological function and prevent death, the entire therapeutic effect (value) of intraoperative irrigation (versus no irrigation) may not be sufficiently comprehensively captured by analysing the primary outcome (rate of reoperations) only. For example, any possible between-group differences in the incidences of deaths and unfavorable functional outcomes may have an effect on the likelihood of a patient being considered for reoperation (i.e., skew the primary analysis).

Prompted by this realization, we deemed it necessary to somehow take into account between-group differences in either mortality and/or unfavorable functional outcome (mRS 0–3 vs. 4–6) in interpreting the findings of the FINISH trial. The approach, to be used in the blinded data interpretation (BDI) [8] of the FINISH trial, is outlined below. In addition, in the event that we will observe a statistically significant difference in the number of deaths

between the two groups, we will carry out a detailed analysis of the causes of death by examining the official death certificates of the participants.

We will claim treatment non-inferiority only if:

- 1) Our primary efficacy analysis, based on the primary outcome, shows non-inferiority and the finding is supported both by the ITT and the PP analyses,
and
- 2) there are no relevant between-group differences in mortality (alive or dead at 6 months) or unfavorable functional outcome (mRS 0–3 vs. 4–6 at 6 months) between the groups (according to an approach outlined in the BDI).

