3.3 Summary of **changes** to the original statistical analysis plan

Original	Final
We will claim non-inferiority of single burr-hole evacuation without irrigation and subdural drainage only if this outcome is supported both by the ITT and the PP analysis.	
We will claim treatment non-inferiority only if:
 
1) Our primary efficacy analysis, based on the primary outcome, shows non-inferiority and the finding is supported both by the ITT and the PP analyses,
 
and

	
2) there are no relevant between-group differences in mortality (alive or dead at 6 months) or unfavorable functional outcome (mRS 0–3 vs. 4–6 at 6 months) between the groups (according to an approach outlined in the BDI).

Exploratory analyses of secondary and other binary endpoints will be performed using the χ^2 test or logistic regression analysis. Continuous outcomes will be analyzed using Student's t-test or analysis of covariance.	Exploratory analyses of secondary and other binary endpoints will be performed using the χ^2 test or logistic regression analysis. Continuous outcomes will be analyzed using regression Student's t-test, analysis of covariance or regression models .
Potential effect modifiers (patient age, unilateral vs bilateral CSDH, use of antithrombotic medication, preoperative mRS and preoperative clinical status, hematoma density, hematoma size and presence of membranes on preoperative imaging) will be analyzed by including interaction terms in statistical models.	
Potential effect modifiers will be analyzed by including interaction terms in statistical models for the following subgroups:
 
 - patient age (<70 years, ≥ 70 years) - GCS score at baseline (9–12, 13–14, 15) - history of head trauma (<4 weeks, ≥ 4 weeks, head trauma with unknown timing, no head trauma) - unilateral versus bilateral CSDH - use of anticoagulation and/or antiplatelet medication versus none - preoperative mRS (0–3, 4–5) - hematoma density (isodense, mixed-density, hypodense) - hematoma size (width in mm) - presence of membranes on preoperative imaging (yes, no)
	
The between-group comparison of 6-month mortality and mRS 4–6 differences will be compared using 85% and 95% CIs (as outlined in the BDI).

The final SAP plan was approved by:

 Jun 27, 2023
 [name] (Jun 27, 2023 00:01 GMT+3) [name] (SCM, methods PI)

 Jun 28, 2023
 [name] (Jun 28, 2023 10:49 GMT+2) [name] (trial statistician)

 Jun 27, 2023

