Acknowledging that the FINISH trial was not powered for assessing differences in mortality or rate of unfavorable functional outcome (mRS 4–6), we used a 3-level hierarchy (**low** / **moderate** / **high**) for expressing our confidence in the possible between-group differences according to the GRADE approach [14–16]. We assumed a 6-month mortality rate of 5% [12,17] and an mRS 4–6 rate of 10% [12]. In terms of **mortality**, the confidence in the estimate was considered **low** if the overall 6-month mortality rate was **<5%**, **moderate** if the overall 6-month mortality rate was **5–10%**, and **high** if the overall 6-month mortality rate was **>10%**. Regarding 6-month unfavorable functional outcome (**mRS 4–6**), the confidence in the estimate was considered **low** if the rate of mRS 4–6 was **<10%**, **moderate** if the rate of mRS 4–6 was **10–15%**, and **high** if the rate of mRS 4–6 was **>15%**.

Our scheme for interpreting the possible safety concerns is outlined in Tables 3 and 4.

Table 3. A priori set thresholds for **concerning** and **alarming** between-group differences in 6-month mortality with associated confidence estimates and pre-determined commitments for interpretation.

Overall mortality in whole population	Confidence in estimate	Threshold for relevant between-group difference in mortality	Resulting action if threshold fulfilled	Authors' interpretation commitment
<5%	Low	Concerning: The 85% confidence interval of the between-group difference in absolute mortality-% does not include 0.0	None	We refrain from making any comments due to the low event rate (low confidence in effect estimate).
		Alarming: The 95% confidence interval of the between-group difference in absolute mortality-% does not include 0.0	Notion on safety concern added to the discussion (not added to the conclusion).	Group A/B was associated with an alarmingly higher mortality rate. Given the event rate, the confidence in this finding was low .
5–10%	Moderate	Concerning: The 85% confidence interval of the between-group difference in absolute mortality-% does not include 0.0	Notion on safety concern added to the discussion (not added to the conclusion).	Group A/B was associated with a concerningly higher mortality rate. Given the event rate, the confidence in this finding was moderate .

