		Alarming: The 95% confidence interval of the between-group difference in absolute mRS 4–6 rate does not include 0.0	Notion on safety concern added to the conclusion.	Group A/B was associated with an alarmingly higher rate of unfavorable functional outcome. Given the event rate, the confidence in this finding was moderate .
>15%	High	Concerning: The 85% confidence interval of the between-group difference in absolute mRS 4–6 rate does not include 0.0	Notion on safety concern added to the conclusion.	Group A/B was associated with a concerningly higher rate of unfavorable functional outcome. Given the event rate, the confidence in this finding was high .
		Alarming: The 95% confidence interval of the between-group difference in absolute mRS 4–6 rate does not include 0.0	Notion on safety concern added to the conclusion.	Group A/B was associated with an alarmingly higher rate of unfavorable functional outcome. Given the event rate, the confidence in this finding was high .

Table 5. Safety concerns for the intention-to-treat dataset.

Variable	All patients (n=??)	Group A (n=??)	Group B (n=??)	Difference (95% CI)	Difference (85% CI)	P-value
6 mo mortality	??/n (??%)	??/n (??%)	??/n (??%)	x (x to x)	x (x to x)	??
6 mo mRS 4–6	??/n (??%)	??/n (??%)	??/n (??%)	x (x to x)	x (x to x)	??

Abbreviations: mRS=modified Ranking Scale, CI=confidence interval

Table 6. Safety concerns for the per-protocol dataset.

Variable	All patients (n=??)	Group A (n=??)	Group B (n=??)	Difference (95% CI)	Difference (85% CI)	P-value
6 mo mortality	??/n (??%)	??/n (??%)	??/n (??%)	x (x to x)	x (x to x)	??
6 mo mRS 4–6	??/n (??%)	??/n (??%)	??/n (??%)	x (x to x)	x (x to x)	??

Abbreviations: mRS=modified Ranking Scale, CI=confidence interval

Imbalance in the incidence of safety concerns (mortality and/or mRS 4–6)?

NO / YES [INCORRECT OPTION TO BE REMOVED]

If NO, the following sentence will be added to the conclusion: “There were no relevant differences in mortality or functional outcome between the groups.”

If YES, interpretation according to **Table 3** (mortality) and **Table 4** (unfavorable functional outcome)

Step 4: Unblinding of treatment groups

Having now considered both the rate of reoperations and safety concerns, we have now reached a consensus on our blinded assessment of efficacy.

Our statistician will now unblind the treatment group assignment (break the randomization code):

- Group A = Irrigation / No irrigation [**INCORRECT OPTION TO BE REMOVED**]

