- Group B = Irrigation / No irrigation [**INCORRECT OPTION TO BE REMOVED**]

Given the above noted, the FINISH data is shown in **Table 1**, **Table 2**, **Table 5 and Table 6** (with n-values for Groups to be added) and in Scenario 1 (**Figure 2**) or Scenario 2 (**Figure 3**). [**INCORRECT OPTION TO BE REMOVED**]. The rate of crossovers is reported here:

- Crossovers from Group A to B, n=?? [**INSERT DATA**]
- Crossovers from Group B to A, n=?? [**INSERT DATA**]

[**COPY TABLE 1 HERE AND INSERT DATA**]

[**COPY TABLE 2 HERE AND INSERT DATA**]

[**COPY TABLE 5 HERE AND INSERT DATA**]

[**COPY TABLE 6 HERE AND INSERT DATA**]

[**COPY FIGURE 2 OR FIGURE 3 HERE**]

Step 5: Unblinded interpretation of treatment effect

Accordingly, our penultimate interpretation of the FINISH trial is as follows:

[CORRECT OPTION TO BE CHOSEN]

Treatment comparison	Primary outcome results	Interpretation based on primary outcome	Between-group difference in safety concerns (mortality, mRS 4-6)	Interpretation commitment regarding safety concerns (mortality, mRS 4-6)
No intraoperative irrigation vs. intraoperative irrigation	Non-inferior	Among adults with symptomatic chronic subdural hematoma who had undergone burr-hole drainage, no intraoperative irrigation was noninferior to intraoperative irrigation in preventing reoperations.	No difference	There were no relevant differences in mortality or functional outcome between the groups.
			Difference	“Interpretation commitment” from Tables 3 and 4 added if criteria for addition to conclusion is fulfilled.
	Superior	Among adults with symptomatic chronic subdural hematoma who had undergone burr-hole drainage, no intraoperative irrigation was superior to intraoperative irrigation in preventing reoperations. However, be it noted that we did not design the study to show superiority.	No difference	There were no relevant differences in mortality or functional outcome between the groups.
			Difference	“Interpretation commitment” from Tables 3 and 4 added if criteria for addition to conclusion is fulfilled.
	Inferior	Among adults with symptomatic chronic subdural hematoma who had undergone burr-hole drainage, no intraoperative irrigation was inferior to intraoperative irrigation in preventing reoperations. However, be it noted that we did not design the study to show inferiority.	No difference	There were no relevant differences in mortality or functional outcome between the groups.

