			Difference	“Interpretation commitment” from Tables 3 and 4 added if criteria for addition to conclusion is fulfilled.
	Inconclusive	Among adults with symptomatic chronic subdural hematoma who had undergone burr-hole drainage, the effect of intraoperative irrigation compared to no intraoperative irrigation in preventing reoperations was inconclusive .	No difference	There were no relevant differences in mortality or functional outcome between the groups.
			Difference	“Interpretation commitment” from Tables 3 and 4 added if criteria for addition to conclusion is fulfilled.

Step 6: Final interpretation

Our final interpretation of the FINISH trial stands as follows:

[COPY PASTE THE CORRECT INTERPRETATION HERE FROM STEP 5]

Place: [ZOOM-/Teams-meeting]
Time: [Insert date here]

[name]
(BDI committee chair)

[name]
(BDI committee co-chair)

[name]
(trial statistician)

[name]
(BDI committee member)

[name], member
(BDI committee member)

Also present at the meeting:

4. References

1. Tommiska P, [name] R, Schwartz C, Kivisaari R, Luostarinen T, Satopää J, et al. Finnish study of intraoperative irrigation versus drain alone after evacuation of chronic subdural haematoma (FINISH): a study protocol for a multicentre randomised controlled trial. *BMJ Open* [Internet]. 2020 [cited 2020 Aug 21];10. Available from: <https://www.ncbi.nlm.nih.gov/pmc/articles/PMC7311024/>
4. van Swieten JC, Koudstaal PJ, Visser MC, Schouten HJ, van Gijn J. Interobserver agreement for the assessment of handicap in stroke patients. *Stroke*. 1988;19:604–7.

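### Section 3.2 makes no relevant difference in mortality or mRS 4–6 a condition for claiming non-inferiority, but the blinded interpretation steps never withhold the claim

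*SAP*

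**What the plan says.** Section 3.2, repeated in the Final column of Section 3.3, opens the decision rule with "We will claim treatment non-inferiority only if". Condition 1 is non-inferiority on reoperation, supported by both ITT and PP. Condition 2 is that "there are no relevant between-group differences in mortality (alive or dead at 6 months) or unfavorable functional outcome" (mRS 4–6 at 6 months), judged by the approach in the BDI. The earlier rule, reproduced in Section 3.1, had only the ITT and PP requirement, so condition 2 was added on purpose.

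Section 4 (BDI) then proceeds as follows.

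- **Step 2** reads efficacy from the reoperation confidence interval alone.
- **Step 3** calls a difference concerning if its 85% CI excludes 0 and alarming if its 95% CI does. Tables 3 and 4 list both under headings such as "Threshold for relevant between-group difference in mortality". The listed actions are nothing, a statement in the discussion, or a statement in the conclusion.
- **Step 5**, non-inferior row, prints one sentence, "no intraoperative irrigation was noninferior to intraoperative irrigation in preventing reoperations", against both the no-difference and the difference sub-rows. In the difference sub-row an interpretation commitment is "from Tables 3 and 4 added if criteria for addition to conclusion is fulfilled".
- **Step 6** is an instruction: "COPY PASTE THE CORRECT INTERPRETATION HERE FROM STEP 5".

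Section 4 also says that the interpretation will not be changed after unblinding.

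**The concern.** Section 3.2 states a gate. Section 4, which produces the trial's published conclusion, treats the same information as an accompanying remark. If a relevant difference in death or disability appears, a reader of Section 3.2 expects no claim, while the committee following Steps 5 and 6 must print that no irrigation was noninferior. The BDI exists to remove this kind of discretion before the code is broken.

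Condition 2 also lacks a usable trigger. Section 3.2 does not say which tier, direction or analysis set makes a difference relevant. The Table 3 and 4 headings suggest that both tiers count, and the two-sided intervals with the Group A/B wording suggest either direction. On that reading a flag whose listed action is to do nothing would still block the claim, and so would a lower mortality without irrigation. The analysis set is simply not named: Table 5 gives ITT results, and the next table is "Table 6. Safety concerns for the per-protocol dataset".

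**Working it through.** **1. Logic trace.** Tables 3 and 4 have three event-rate bands × two thresholds × two outcomes = 12 cells. Suppose the reoperation criterion is met in ITT and PP.

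| Action in Tables 3–4 | Cells | Step 5–6 conclusion | Section 3.2, if the difference is relevant |
|---|---|---|---|
| None | 2 | noninferior | not claimed |
| Discussion only | 4 | noninferior | not claimed |
| Conclusion | 6 | noninferior, plus safety statement | not claimed |

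None of the 12 cells withholds the claim, not even an alarming difference held with high confidence.

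**2. The SAP's own design figures.** With reoperation 9.6% in both arms, margin 7.5%, one-sided alpha 0.025 and 80% power:

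n = 2 × 0.096 × 0.904 × (1.960 + 0.842)² / 0.075² = 242.2, so 243 per arm, as stated. Then 486/(1 − 0.10) = 540, and 486/(1 − 0.157) = 576.5, which the SAP rounds to 578. No sample-size error bears on this point.

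**3. How often the two passages diverge.** I used 400,000 simulated trials with 289 per arm, reoperation 9.6% in both arms and 15.7% of patients removed at random for PP. Mortality was 5% and mRS 4–6 10% (the rates assumed in Section 4), with deaths counted within mRS 4–6. Assumptions of mine: unstratified Wald intervals, and reoperation independent of death and mRS.

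The reoperation criterion is met in both ITT and PP with probability 0.785. The table gives the share of trials where it is met and an ITT safety flag is also present.

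| What counts as relevant | No true difference, either direction | No true difference, excess without irrigation only | 8% v 5% mortality and 13% v 10% mRS 4–6, either direction |
|---|---|---|---|
| any 85% CI flag | 18.5% | 9.2% | 46% |
| any 95% CI flag | 6.6% | 3.3% | 29% |
| conclusion-level cells only | 3.6% | 1.8% | 27% |

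The last column is illustrative; those differences are not in the SAP. As a cross-check, at least one ITT flag occurs in 23.7% (85% CI) or 8.4% (95% CI) of trials with no true difference. Under independence 0.785 × 0.237 = 0.186 and 0.785 × 0.084 = 0.066, in agreement with the table.

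Of the 18.5%, 5.4 points are trials whose only flags carry the action None. With no true difference, the criterion is met and the ITT and PP 85% CI flags disagree in 10.4% of trials, so the unnamed analysis set matters.

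**4. Worked example.** Take 20 v 8 deaths among 289 per arm.

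- Overall mortality: 28/578 = 4.84%, the low-confidence band.
- Difference: 6.92% − 2.77% = 4.15 points.
- SE = √(0.0692 × 0.9308/289 + 0.0277 × 0.9723/289) = 1.78 points.
- 95% CI: 4.15 ± 1.960 × 1.78 = 0.67 to 7.64. 85% CI: 1.59 to 6.71.

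This is alarming. Table 3 assigns "Notion on safety concern added to the discussion (not added to the conclusion". Unless Table 4 separately requires a statement, the conclusion reads noninferior with no safety qualification. If alarming counts as relevant, Section 3.2 forbids the claim.

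**The case against.** The best defence is that these are two different claims. Section 3.2 speaks of treatment non-inferiority and lists the reoperation result as only one ingredient. Step 5 prints its sentence in a column based on the primary outcome and limits it to preventing reoperations. On that reading Step 5 reports condition 1 and contradicts nothing. The distinction is real, but Steps 5 and 6 then contain no place where the overall claim is made or refused, although Step 6 is labelled the final interpretation. Condition 2 would govern a claim that the procedure never reaches.

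Other points on that side:

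- **The BDI defines the trigger.** For tier and direction this is largely fair: the printed wording points to both tiers and either direction, so the one-direction figures describe a rule that the SAP does not print. Deferring to the BDI lets it define relevant; it does not turn a necessary condition into an added remark. The analysis set stays open.
- **The flow chart in Section 4 is not in the text at hand.** A withholding branch there cannot be excluded, but it would conflict with Steps 5 and 6, which are printed in full.
- **The largest percentages use the widest trigger.** True; the conclusion-level figure is 3.6%.
- **The safety information is not lost.** Also true. A difference removes the sentence saying that there were none, alarming mortality in the example must be discussed, and Section 3.2 commits to a death-certificate review if deaths differ significantly. The mRS 4–6 comparison, which includes deaths, could separately put a statement in the conclusion. The reoperation margin and its type I error are untouched.

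**Conclusion.** The concern holds and must be fixed before unblinding. The stated decision rule and the procedure that writes the conclusion give different answers on the same data whenever the reoperation criterion is met alongside a relevant safety difference. By chance alone this happens in 3.6% to 18.5% of trials, depending on the tier that counts (ITT, either direction). Under the illustrative true differences it happens in 27% to 46%. These shares rest on the SAP's assumed event rates, 289 per arm, unstratified Wald intervals and independence of reoperation from the safety outcomes. The contradiction itself rests only on the printed text.

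**What to change.** Choose one of two routes and record it before unblinding.

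**(a) Make condition 2 a reporting commitment.** In Sections 3.2 and 3.3, replace it with wording such as: *Relevant differences in 6-month mortality or mRS 4–6 do not alter the non-inferiority claim for reoperation; they are reported with it as set out in Tables 3–4 and Step 5.* This changes wording only and loses no power. It does drop a pre-specified condition and permits claims that Section 3.2 now refuses, so the change should be stated openly.

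**(b) Keep condition 2 as a gate.** Rewrite the Step 5 cell for non-inferior with a difference, for example: *The reoperation criterion was met, but treatment non-inferiority is not claimed because of a relevant difference in [mortality / mRS 4–6].* Also name the tier, the direction and the analysis set (Table 5 or Table 6) that trigger it. The cost is a lower chance of a claim when there is no true safety difference, starting from 0.785:

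| Trigger | Chance of claiming non-inferiority |
|---|---|
| 85% CI, ITT or PP, either direction | 0.785 − 0.239 ≈ 0.55 |
| 85% CI, ITT, either direction | 0.785 − 0.185 = 0.60 |
| 85% CI, ITT, excess without irrigation only | 0.785 − 0.092 ≈ 0.69 |
| 95% CI, ITT, either direction | 0.785 − 0.066 ≈ 0.72 |
| 95% CI, ITT, excess without irrigation only | 0.785 − 0.033 ≈ 0.75 |
| conclusion level, ITT, either direction | 0.785 − 0.036 ≈ 0.75 |

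Neither route needs new data.

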2.1 Background and Objectives

Chronic subdural hematoma (CSDH) is the most common type of intracranial hemorrhage and one of the most common diagnoses necessitating neurosurgical care. The incidence of CSDH is sharply rising due to diagnostic improvements and the aging population. The standard care for CSDHs in most countries is a surgical procedure called burr-hole evacuation (craniostomy), followed by intraoperative irrigation and placement of a subdural drain. However, there is a possibility that intraoperative irrigation may not be required, as it potentially leads to increased risks of infections, rebleeding, and patient distress during the procedure performed under local anesthesia. There is also evidence to suggest that irrigation *per se* may be harmful.

We conducted a pragmatic randomized, parallel-group, non-inferiority trial comparing burr-hole craniostomy with intraoperative irrigation and 48h of subdural drainage to the same treatment but with no intraoperative irrigation, with a primary objective to assess the therapeutic value of intraoperative irrigation. We chose the rates of reoperation in the two groups, as an indicator for recurrence of symptomatic CSDH within 6 months.

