Summary statistics will be presented for both groups. Continuous variables will be presented in terms of mean values or medians with SDs and IQRs, respectively. Categorical variables will be presented with relative frequencies in percent.

The results from the statistical analysis will be considered to support a claim of non-inferiority if the upper limit of a one-sided 97.5% CI (or equivalently a 95% two-sided CI) excludes a difference in the primary endpoint in favor of the irrigation group of more than 7.5%. The center stratification of the randomization will be accounted for in the calculation of the CI.

Exploratory analyses of secondary and other binary endpoints will be performed using the χ^2 test or logistic regression analysis. Continuous outcomes will be analyzed using regression Student's t-test, analysis of covariance or regression models.

Potential effect modifiers will be analyzed by including interaction terms in statistical models for the following subgroups:

- patient age (<70 years, \geq 70 years)
- GCS score at baseline (9–12, 13–14, 15)
- history of head trauma (<4 weeks, \geq 4 weeks, head trauma with unknown timing, no head trauma)
- unilateral versus bilateral CSDH
- use of anticoagulation and/or antiplatelet medication versus none
- preoperative mRS (0–3, 4–5)
- hematoma density (isodense, mixed-density, hypodense)
- hematoma size (width in mm)
- presence of membranes on preoperative imaging (yes, no)

The primary endpoint will be investigated as described above using a CI, which is equivalent to using a non-inferiority test with a one-sided p-value of 0.025 (or a two-sided of 0.05). The between-group comparison of 6-month mortality and mRS 4–6 differences will be compared using 85% and 95% CIs (as outlined in more detail in the BDI). The statistical testing of other endpoints will also be performed using a two-sided significance level of 0.05.

STATA (Statistics/Data analysis, SE v15.1, StataCorp LLC, [name]) will be used for analyses.

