Given that the objective of surgery for CSDH extends beyond preventing reoperations to also encompass the improvement of neurological function and prevention of death, the entire treatment effect of intraoperative irrigation (versus no irrigation) may not be adequately captured by focusing solely on the primary outcome measure, the rate of reoperations. We deemed it crucial to also consider the potential impact of between-group differences in deaths and/or unfavorable functional outcomes, as both could have an effect on the rate of reoperations. We felt that in the name of transparency and trustworthiness, we would need to define *a priori* thresholds for between-group differences in mortality and rate of unfavorable functional outcome (mRS 4–6) at 6-months that we consider “concerning” or “alarming”.

We considered a difference to be “concerning” if the 85% confidence interval (CI) of the absolute between-group difference in mortality or rates of unfavorable functional outcome (mRS 4–6) did not encompass the value of 0.0 and “alarming” if the 95% CI of the absolute between-group difference in mortality or mRS 4–6 rates did not encompass the value of 0.0.

Prior to establishing the thresholds for the 85% CI (“concerning”) and 95% CI (“alarming”) thresholds, we conducted simulations to ensure that these thresholds would yield clinically relevant differences in mortality and unfavorable functional outcome (mRS 4–6) (Figure 4). For the mortality simulations, we assumed a mortality rate of 5% in the standard care group. This selection was based on two recent similar-sized RCTs, in similar settings (Sweden [11], UK [12]), where the 6-month mortality rate was 5% in the groups treated with burr-hole craniostomy and subdural drainage. As for the mRS 4–6 simulations, we assumed an mRS 4–6 rate of 10% based on the results of the DEX-CSDH [12] and DESCA trials [13].

[figure not shown]

Figure 4. Simulation of the 95% (left panel) and 85% (right panel) confidence intervals for between-group differences in 6-month mortality rates (upper panel) and rates of mRS 4–6 (lower panel). The difference in mortality and/or rates of mRS 4–6 is significant if the 85% CI or 95% CI does not encompass the value of 0.0.

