		Alarming: The 95% confidence interval of the between-group difference in absolute mortality-% does not include 0.0	Notion on safety concern added to the conclusion.	Group A/B was associated with an alarmingly higher mortality rate. Given the event rate, the confidence in this finding was moderate .
>10%	High	Concerning: The 85% confidence interval of the between-group difference in absolute mortality-% does not include 0.0	Notion on safety concern added to the conclusion.	Group A/B was associated with a concerningly higher mortality rate. Given the event rate, the confidence in this finding was high .
		Alarming: The 95% confidence interval of the between-group difference in absolute mortality-% does not include 0.0	Notion on safety concern added to the conclusion.	Group A/B was associated with an alarmingly higher mortality rate. Given the event rate, the confidence in this finding was high .

Table 4: A priori set thresholds for concerning and alarming between-group differences in 6-month mRS4–6 with associated confidence estimates and pre-determined commitments for interpretation

Overall mRS 4–6 in whole population	Confidence in estimate	Threshold for relevant between-group difference in mRS 4–6	Resulting action if threshold fulfilled	Authors' interpretation commitment
<10%	Low	Concerning: The 85% confidence interval of the between-group difference in absolute mRS 4–6 rate does not include 0.0	None	We refrain from making any comments due to the low event rate (low confidence in effect estimate).
		Alarming: The 95% confidence interval of the between-group difference in absolute mRS 4–6 rate does not include 0.0	Notion on safety concern added to the discussion (not added to the conclusion).	Group A/B was associated with an alarmingly higher rate of unfavorable functional outcome. Given the event rate, the confidence in this finding was low .
10-15%	Moderate	Concerning: The 85% confidence interval of the between-group difference in absolute mRS 4–6 rate does not include 0.0	Notion on safety concern added to the discussion (not added to the conclusion).	Group A/B was associated with a concerningly higher rate of unfavorable functional outcome. Given the event rate, the confidence in this finding was moderate .

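### Condition 2 of the non-inferiority claim has no direction, so as section 3.2 is written, fewer deaths or less disability without irrigation would fail it

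*SAP*

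**What the plan says.** Section 3.2 opens the claim rule with "We will claim treatment non-inferiority only if" and lists two conditions. The first is non-inferiority on reoperations in both the ITT and PP analyses. The second is that "there are no relevant between-group differences in mortality (alive or dead at 6 months) or unfavorable functional outcome" (mRS 0–3 v 4–6), "according to an approach outlined in the BDI". The Final column of section 3.3 repeats the rule. Neither place gives a direction.

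Section 3.2 adds that "6-month mortality and mRS 4–6 differences will be compared using 85% and 95% CIs". Step 3 of the BDI makes this operational. A difference is concerning if the 85% CI, and alarming if the 95% CI, "of the absolute between-group difference in mortality or mRS 4–6 rates did not encompass the value of 0.0". Tables 3 and 4 cover either arm: the committed sentence for an alarming difference begins "Group A/B was associated with an alarmingly higher mortality rate". The NO/YES question that closes Step 3 asks only whether there is an imbalance.

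Step 5 has one non-inferior sentence, shared by the No difference and Difference rows. After a difference it adds a commitment from Tables 3 and 4 where their criteria for the conclusion are met. It does not withdraw the sentence.

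On the background, section 2.1 says of irrigation that "it potentially leads to increased risks of infections, rebleeding, and patient distress during the procedure performed under local anesthesia", and that it may in itself be harmful.

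**The concern.** Non-inferiority is a claim in one direction: the new treatment is not unacceptably worse. Condition 1 respects this, because only a difference favouring irrigation by more than 7.5% defeats it. Condition 2 does not. It treats fewer deaths without irrigation exactly like more deaths without irrigation.

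This matters because the rule governs the trial's headline claim. Under section 3.2, a trial with reoperations inside the margin and clearly fewer deaths without irrigation could not claim non-inferiority. Chance differences in the favourable direction would have the same effect when the arms are truly identical. Since section 2.1 raises possible harm from irrigation, the favourable direction is foreseeable.

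**Working it through.** **1. The plan's own figure.** With reoperation 9.6% in both arms, margin 7.5%, one-sided alpha 0.025 and 80% power:

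n = (1.96 + 0.8416)² × 2 × 0.096 × 0.904 / 0.075² = 7.849 × 0.173568 / 0.005625 = 242.2, so 243 per group, as section 2.9.1 states.

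Section 2.9.2 then gives 486 / (1 − 0.157) = 576.5, taken up to 578, or 289 per group. The checks below use 289.

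**2. Do the stated reasons support a two-sided bar?** Section 3.2 gives two.
- *Skewing.* Deaths and poor outcomes may change who is considered for reoperation. If patients who die or do badly are less often reoperated, fewer such patients without irrigation leaves more candidates for reoperation in that arm. That works against non-inferiority, so a claim that still succeeds has not been helped by it.
- *Incomplete capture.* Reoperation alone may miss part of the treatment's value. If deaths or disability are fewer without irrigation, the missing part favours no irrigation.

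Both are reasons to look at and report a difference in either direction. Neither is a reason to refuse the claim when the difference favours no irrigation.

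**3. How small a favourable difference fails the condition?** Wald CI: d ± z √[p₁(1−p₁)/289 + p₂(1−p₂)/289], with z = 1.44 (85%) or 1.96 (95%).
- Mortality, 14/289 with irrigation (about 5%): 7/289 without irrigation is a difference of 2.4 points and the 85% CI excludes zero. At 5/289 (3.1 points) the 95% CI does.
- mRS 4–6, 29/289 with irrigation (about 10%): 19/289 (3.5 points) and 16/289 (4.5 points) respectively.

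With 7 v 14 deaths, overall mortality is 21/578 = 3.6%. That is the low stratum of Table 3, where a concerning difference leads to no action. The table lists it as a threshold for a relevant difference and yet does nothing with it, so what counts as relevant is not settled.

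**4. How often?** Simulation of two arms of 289 (400,000 trials), each patient dead, alive at mRS 4–5, or other, so that deaths are nested in mRS 4–6. Wald CIs, no centre stratification, one analysis set. The rule trips if either outcome meets the criterion.

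| What counts as relevant | Identical arms (5% / 10%): either direction | Identical arms: favouring no irrigation | Assumed benefit (3% v 5%, 8% v 10%): favouring no irrigation |
|---|---|---|---|
| Any 85% CI excluding zero | 24% | 12% | 48% |
| Only rows of Tables 3–4 with an action | 17% | 8% | 31% |
| Only a 95% CI excluding zero | 8% | 4% | 28% |
| Only rows that put text in the conclusion | 5% | 2% | 6% |

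The 5% and 10% are the SAP's own rates (BDI Step 3). The 3% and 8% without irrigation are illustrative and not from the SAP. Under that benefit, a rule counting only harm from no irrigation would trip in about 1.4% of trials at the 85% level and 0.3% at the 95% level.

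**The case against.** The strongest objection is that the claim would not in fact be barred. Condition 2 defers to the BDI, and no BDI step withdraws a non-inferior conclusion. Step 5 keeps the sentence and adds text, and Step 6 copies it. This stands as a limit: a reader might infer that the trial is bound to lose its claim after a favourable difference, but only section 3.2 says so. It does not rescue condition 2. Section 3.2 is the stated claim rule, and enforcing it in Step 5 without adding a direction would let a benefit block the claim.

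Second, the size depends on the reading of relevant. That stands, and the table shows the range. The 85% row alone would overstate it.

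Third, the SAP's reasons for condition 2 are worded without direction, and the skewing argument is clearer for deaths than for survivors at mRS 4–5, because the SAP does not say which way poor function shifts the decision to reoperate. This supports examining and reporting both directions. It does not support refusing the claim when outcomes are better.

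Two further inferences should not be drawn. A reader might say the rule penalises the very benefit the trial was set up to find. Section 2.1 describes a non-inferiority trial judged by reoperations. The harms it names are infection, rebleeding and distress, and section 2.7 describes mortality and mRS as unpowered and originally exploratory. A reader might also multiply the 80% power by the chance of passing condition 2 to get an overall chance of a claim. That would combine power at 243 per group with a check at 289, and would assume independence although section 3.2 expects deaths to affect reoperation.

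**Conclusion.** The point holds for section 3.2 and its repetition in 3.3: condition 2 has no direction, and by its terms a relevant advantage of no irrigation defeats the claim that no irrigation is non-inferior. Step 5 does not carry this out, so the document also disagrees with itself on whether condition 2 is a gate at all.

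Half of all chance triggers under identical arms are of the favourable kind: about 12%, 8% or 4% of trials for the first three readings of relevant, and 2% if only text reaching the conclusion counts. Under the illustrative benefit the corresponding figures are 48%, 31%, 28% and 6%. They rest on 289 per arm, Wald intervals, the SAP's 5% and 10% rates with irrigation, and a single analysis set. Tables 5 and 6 report both ITT and PP; applying the check to both could only raise the trigger rates.

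**What to change.** Before the blinded interpretation meeting:
- **Sections 3.2 and 3.3.** Reword condition 2 so that only a relevant difference to the disadvantage of no irrigation bars the claim. For example: neither 6-month mortality nor the mRS 4–6 rate is higher in the no-irrigation group by a difference that counts as relevant.
- **Define relevant once.** Name the single CI level, or the rows of Tables 3 and 4, that decide the condition.
- **Step 3.** Answer the imbalance question separately under Scenario 1 (Group A is no irrigation) and Scenario 2 (Group B is), as Step 2 already does for reoperations. Blinding is kept.
- **Step 5.** Make the Difference row follow the same rule, so that it and section 3.2 give the same conclusion.
- **Reporting.** Differences favouring no irrigation are still reported under Tables 3 and 4; they do not bar the claim.

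The cost is one sentence in 3.2 and 3.3, a line per scenario in Step 3 and an aligned Step 5. No new data or analyses are needed.
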